A silver lining in the VAD sky NCT 05163392 03/24/2025

Impact of silver dressing on LVAD associated driveline infection

Objective

Driveline Infection remain a prevalent complication of LVAD therapy with rates varying between 10% and an astounding 50% depending on VAD centers report. Driveline dressing protocols vary widely between centers and to date no randomized control trial (the gold standard for treatment evaluation) has been carried out. Our aims are twofold:

- To evaluate the effectiveness of a silver-based driveline dressing protocol to reduce DLI
 as measured by DLI rate. Secondary goals measured will be DLI speciation, driveline site
 dermatitis rate, comfort, ease of use, protocol compliance and cost.
- To evaluate the feasibility of a multi-center RCT that would help establish a widely accepted consensus on driveline dressing practices

The physical and psychological burdens of driveline maintenance, driveline infection and allergic reactions to dressing kits components remain a major barrier to improved VAD patient's life expectancy and quality of life. No widely accepted protocols exist and no prospective randomized clinical trials to date have been carried out to evaluate a specific driveline dressing protocol.⁴

We posit that a silver-based dressing with weekly changes will reduce the rate of DLI and allergic reaction while improving patients' comfort and quality of life. Moreover, we hope that a prospective RCT, the gold standard for treatment evaluation, will catalyze the standardization of dressing change protocols across VAD centers. In this spirit we will broaden this single center trial to a multi-center trial to increase the significance and analytical power of the study.

Methods

This prospective research clinical trial will be conducted in a single academic medical center. The enrollment period is between January 1st, 2022 and December 31st, 2023. The initial follow-up period will be closed on December 31st 2023 with a continuation of the follow-up until December 31st 2024. Patients will be selected from current LVAD patients followed by our medical center clinic and from patients implanted with LVAD at our center during the study enrollment timeframe. Patients will be randomly assigned to the control protocol and the silver protocol. Both protocols will be taught to the patients and nursing staff by the VAD coordinators. The comparative evaluation will be done through adverse event collection, driveline culture results, patient survey and DL photos at specific intervals.

A. Inclusion Criteria

The following patients will be included in the study:

- >18 years of age
- Implanted with LVAD as DT or BTT at the Academic Medical Center with implantation scheduled between January 1st, 2022 and December 31st, 2023
- Implanted prior to January 1st 2022 with no history or signs and symptoms of DLI as of January 1st 2022.

B. Exclusion criteria

The following will be excluded from the study. Patients with

- A history of DLI
- A history of sternal wound infection
- Implantation secondary to VAD exchange for device infection

C. Interventions

A new driveline dressing kit will be trialed on patients randomized to the intervention arm of the study. Both arms will have a regular dressing kit and a sensitive dressing kit.

The trial arm kits include:

- a. For standard dressing: a silverlon antimicrobial patch, CHG swabs for cleaning, an occlusive dressing with window, and driveline anchors. The driveline dressing change frequency will be weekly.
- b. For sensitive skin dressing: a silverlon antimicrobial patch, Providone/iodine swabs for cleaning, an occlusive dressing with window, and sensitive driveline anchors. The driveline dressing change frequency will be weekly.

The control arm kits include:

- a. For standard dressing: No antimicrobial barrier, CHG swabs for cleaning, an occlusive dressing with window, and driveline anchors. The driveline dressing change frequency will be every 96 hours.
- b. For sensitive skin dressing: No antimicrobial barrier, Providone/iodine swabs for cleaning, an occlusive dressing with window, and driveline anchors. The driveline dressing change frequency will be every 96hr.

D. Assessment

The following endpoints will be assessed for patients in both arms of the study enrolled between 01/01/2022 and 12/31/2023 and comparison will be drawn between the 2 groups:

- 1. DLI rate in number per 100-patient month
- 2. Time to first DLI in days

E. Data Management

Data is collected by the PI and analyzed by our data analyst. Additionally, cost data will be collected via our purchasing analyst who will retain data on number ok kits sent to each patient. Patients will be deidentified for all data collection. Data is stored behind the medical center firewall and encryption software. Data is accessible to the PI, the data analyst and our medical director.

F. Statistical Analysis Plan (SAP)

Study Design:

A randomized controlled trial (RCT) in which patients are randomly assigned to one of two groups:

- a. Silver Dressing Group
- b. Standard Dressing Group

Primary Outcome:

 Rate of driveline infection in number per 100 patient month, defined as number of driveline cultures positive for bacterial infection per 100 months of patients on support.

Secondary Outcome(s):

 Mean time to first driveline infection, defined as a number of days to first positive culture.

Covariates to Control for:

- Body Mass Index (BMI)
- Gender

INTERMACS Level

Statistical Analysis Overview:

The analysis will focus on univariate tests to assess the differences between silver dressing and standard dressing groups, while controlling for covariates such as BMI, gender, and INTERMACS level. The significance level for all analyses will be set at p < 0.05.

Data Cleaning and Assumptions:

- Missing data will be addressed using appropriate techniques, such as multiple imputation or complete case analysis, depending on the nature and extent of missing data.
- Assumptions of normality will be assessed for continuous variables, and non-parametric tests will be considered for non-normally distributed data.

Univariate Analysis:

- For continuous outcomes, descriptive statistics (mean, standard deviation) will be presented
 for each treatment group. Between-group comparisons will be made using a two-sample ttest (if data are normally distributed) or a Mann-Whitney U test (if data are non-normally
 distributed).
- For categorical outcomes, descriptive statistics (frequencies and percentages) will be presented for each group. Between-group comparisons will be conducted using the chisquare test or Fisher's exact test, as appropriate.
- Univariate analysis will focus on comparing the primary and secondary outcomes between the two treatment groups, without adjusting for covariates.

Multivariate Analysis (Controlling for Covariates):

- Linear regression will be used to compare the treatment effects while adjusting for BMI, gender, and INTERMACS level. These covariates will be included as fixed effects in the model.
- The significance level for all covariates will be set at p < 0.05 in the final model, following a backward elimination procedure, if necessary, to identify the most relevant covariates.

Model Assumptions and Diagnostics:

The assumptions for each regression model will be checked. For linear regression, normality
of residuals, linearity, and homoscedasticity will be assessed.

Sensitivity Analyses:

 Sensitivity analyses will be conducted to evaluate the robustness of the results by varying handling strategies for missing data and by testing the impact of potential outliers.

Statistical Software:

• All analyses will be conducted using SAS version 9.4.

Data Handling and Quality Assurance

- Data is collected by the PI and analyzed by our data analyst. Patients are deidentified for all data collection. Data is stored behind the medical center firewall and encryption software. Data is accessible to the PI, the data analyst and our medical director.
- Outliers and implausible values will be reviewed and resolved.

Reporting

- Results will be reported in accordance with CONSORT guidelines.
- Findings will be disseminated through peer-reviewed publications and conference presentations.

[figure not shown]
Conclusion:

The statistical analysis will provide insight into the comparative effectiveness of silver dressing versus standard dressings while controlling for potential confounders such as BMI, gender, and INTERMACS level. The univariate analysis will provide preliminary insights into dressing effect,

with multivariate models ensuring a more rigorous adjustment for confounding variables. All analyses will be conducted at a significance level of p < 0.05.

References

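### Earlier implants, who had to be DLI-free at 1 January 2022, are pooled with new implants, and time on support is neither a stated stratification factor nor a covariate

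*Combined protocol and SAP*

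**What the plan says.** The Methods describe the source population in one sentence: "Patients will be selected from current LVAD patients followed by our medical center clinic and from patients implanted with LVAD at our center". Section A (Inclusion Criteria) then sets two routes of entry. One is for new implants: "Implanted with LVAD as DT or BTT at the Academic Medical Center with implantation scheduled between January 1st, 2022 and December 31st, 2023". The other is for patients already on support: "Implanted prior to January 1st 2022 with no history or signs and symptoms of DLI as of January 1st 2022". The exclusions in section B, for past DLI and past sternal wound infection, apply to everyone.

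On allocation, the Methods say "Patients will be randomly assigned to the control protocol and the silver protocol". Section F repeats that assignment is random. Neither place gives a ratio, block scheme or stratification factor.

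On analysis, section F lists three covariates and uses them as follows: "Linear regression will be used to compare the treatment effects while adjusting for BMI, gender, and INTERMACS level". These may then be reduced "following a backward elimination procedure, if necessary, to identify the most relevant covariates". The other comparison is unadjusted: "Univariate analysis will focus on comparing the primary and secondary outcomes between the two treatment groups, without adjusting for covariates". The sensitivity analyses are limited to "varying handling strategies for missing data and by testing the impact of potential outliers". Implant cohort and time since implant do not appear as a stratum, covariate, subgroup or sensitivity analysis.

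**The concern.** The second route selects patients on the outcome the trial measures. A patient implanted well before 2022 qualifies only by having spent all that time on support without a DLI. A new implant has had little or no driveline exposure in which to fail the same test. If the risk of a first DLI varies with time on support, or if those who have stayed infection-free are a lower-risk group, the two cohorts have different expected rates.

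With few patients, the mix of cohorts can differ between arms by chance. Any such difference feeds into the comparison of rates per 100 patient-months, and none of the three listed covariates is designed to remove it. Even when the arms are balanced, a model that ignores a prognostic variable gives up some precision. The pooled result also gives no reading by cohort, which would help anyone using the trial to plan the multi-centre study named in the Objective.

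**Working it through.** The documents state no sample size, event count, cohort split or cohort-specific DLI rate, so there is no plan figure to reproduce. What follows is an illustration.

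**Assumed inputs (none in the documents).** Half the patients are new implants; allocation is 1:1; follow-up is equal; the dressing has no true effect. N is 40, 60 or 100. New implants have k = 1.5, 2 or 3 times the DLI rate of earlier implants.

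**1. Chance imbalance.** With n = N/2 per arm and N/2 new implants in all, the number of new implants X in one arm is hypergeometric. The difference in new-implant share between arms is d = (2X − n)/n.

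| N | Split giving 20 points | Probability of a difference of 20 points or more |
|---|---|---|
| 40 | 12 v 8 of 20 | 34% |
| 60 | 18 v 12 of 30 | 20% |
| 100 | 30 v 20 of 50 | 7% |

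If new implants are 30% or 70% of patients, the probabilities are 30%, 16% and 5%. With an even split they fall to 2% at N = 150 and 0.7% at N = 200.

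**2. Spurious rate ratio.** With new-implant shares pA and pB and no dressing effect, the ratio is (1 + pA(k − 1)) / (1 + pB(k − 1)). At N = 60, take a split of 19 v 11. A split this uneven or worse, in either direction, has exact probability 7.0%.

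- k = 1.5: (30 + 9.5)/(30 + 5.5) = 39.5/35.5 = 1.11
- k = 2: (30 + 19)/(30 + 11) = 49/41 = 1.20
- k = 3: (30 + 38)/(30 + 22) = 68/52 = 1.31

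So about 7% of 60-patient trials show a ratio at least this large, or its inverse, from imbalance alone.

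**3. Size beside event-count noise.** Further assumptions: 1 DLI per 100 patient-months in earlier implants, 18 months per patient, N = 60, Poisson counts.

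- Events at k = 2: 30 × 18 × 0.01 = 5.4 in earlier implants plus 30 × 18 × 0.02 = 10.8 in new ones, so 16.2 in all and 8.1 per arm.
- Noise variance of the log rate ratio: 2/8.1 = 0.247. The 95% range is exp(±1.96 × √0.247), about 0.38 to 2.65.
- Variance of d: 0.0169. Imbalance variance of the log rate ratio, approximately: 0.0169 × ((k − 1)/((k + 1)/2))². At k = 2 this is 0.0169 × (1/1.5)² = 0.0075.
- Share of the total at k = 2: 0.0075/(0.247 + 0.0075) = 3%.
- At k = 3 there are 10.8 events per arm: noise 2/10.8 = 0.185, imbalance 0.0169 × (2/2)² = 0.0169, share about 8%.

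**4. Type I error.** Simulation under the same event-rate assumptions (20,000 runs per setting; N = 60, 100, 200; k = 1.5, 2, 3; two-sided 0.05), averaged over all randomisations, gives 0.046 to 0.065 for the unadjusted rate test. Conditional on a 20-point imbalance it is 0.055, 0.066 and 0.078 at k = 2, and 0.081, 0.093 and 0.138 at k = 3, for N = 60, 100 and 200. A test stratified by cohort gives 0.049 to 0.051 in these conditional cases.

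**The case against.** The strongest reply is that randomisation already does what is needed. Over repeated trials there is no bias, and the simulated type I error stays close to nominal. Inflation appears only once a large imbalance is fixed, and the highest value, 0.138, pairs a 20-point imbalance with 200 patients, where such an imbalance occurs in 0.7% of trials. Beside a noise range of 0.38 to 2.65, a shift of 1.20 is small. All of this stands, and it limits the point to conditional imbalance and lost precision.

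Several stronger readings are tempting and are not supported:

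- A reader might infer that allocation was simple and unstratified. The documents say only that it was random; they do not state the method, and a figure is missing from the text available here.
- A reader might infer that implant cohort is a major DLI risk factor, through a healed exit site or a settled dressing routine. The documents mention neither. The 10% to 50% range in the Objective is across centres, not by time on support.
- A reader might take the sternal wound exclusion as a second difference between cohorts. It applies to all patients. Nor do the documents say how soon after implant new patients are randomised.

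It may also be said that the SAP overview presents its covariates as examples, which leaves room for another. The list that follows names only three, and an addition made after results are known would be post hoc. Finally, no objective is specific to new implants and rates within cohort would be imprecise. That is fair, and it is why the table proposed below is descriptive only.

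**Conclusion.** The point holds in a limited form. The eligibility criteria create a baseline split tied to prior freedom from the primary outcome, and neither the stated randomisation nor the SAP makes use of it. The consequence is an uncorrected chance imbalance and some lost precision, not systematic bias.

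The size depends on three unknowns: the number of patients, the cohort split and the ratio of DLI rates between cohorts. On the assumptions shown, a 20-point imbalance is fairly common up to about 60 patients and uncommon from 150. At 60 patients, imbalance contributes about 3% to 8% of the log rate ratio variance when new implants have two to three times the rate. A reader might infer that the trial's result would be unreliable without this change; those figures do not support that. The improvement is modest but costs almost nothing, so it should be made.

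**What to change.** In section F, add time since implant at randomisation to the covariate list. Implant cohort (before, or on or after, 1 January 2022) is an acceptable alternative, but it separates late-2021 from early-2022 implants that are nearly alike. Keep the covariate in the adjusted model for both outcomes, whatever form that model finally takes, and exempt it from backward elimination. State how allocation was done and, if it was stratified, by what.

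Report DLI per 100 patient-months by arm within each cohort as a descriptive table, without tests. In the multi-centre extension, stratify randomisation by cohort.

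The cost is one degree of freedom and one table; implant date is already needed to apply the eligibility criteria. The real drawback is timing. The document is dated 24 March 2025, after follow-up was due to end on 31 December 2024. The SAP should therefore give the date of the addition and say whether outcome data had been seen. If they had, the adjusted result must be labelled as a late addition.

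### The SAP's primary outcome counts positive cultures with no rule for repeats, so read literally it gives a culture rate and not the driveline infection (DLI) rate named in the objective

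*Combined protocol and SAP*

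**What the plan says.** The Objective sets out to reduce DLI "as measured by DLI rate". Section D (Assessment) lists as its first endpoint "DLI rate in number per 100-patient month". Neither place defines a DLI.

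The SAP (Section F, Primary Outcome) keeps the infection-rate label but gives the numerator and denominator as "defined as number of driveline cultures positive for bacterial infection per 100 months of patients on support". The secondary outcome is "Mean time to first driveline infection, defined as a number of days to first positive culture".

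The analyses named are:
- For continuous outcomes, a t-test or Mann-Whitney test. Under Data Cleaning and Assumptions, "non-parametric tests will be considered for non-normally distributed data".
- For adjustment, one model: "Linear regression will be used to compare the treatment effects while adjusting for BMI, gender, and INTERMACS level".
- Sensitivity analyses limited to "varying handling strategies for missing data and by testing the impact of potential outliers".

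Nowhere is there an infection-free interval, a new-organism rule, a cap per episode or per patient, adjudication, or a stated indication for taking a culture. Nothing ends a patient's follow-up at the first on-study DLI.

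**The concern.** The unit counted is a culture, while the unit in the objective is an infection. Under the written rule, one patient with three positive cultures in a single infection scores 3, the same as three patients with one infection each. The secondary outcome is limited to the first positive culture and so is safe from repeat counting; the primary outcome has no such limit. Two analysts could apply the sentence to the same records and report different primary results, and the planned sensitivity analyses would not show why.

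Three things are at stake:
- The headline rate is inflated.
- Precision is lost in any analysis that uses the counts directly.
- The arm comparison is biased, in either direction, if cultures per infection differ by arm. Visibly different kits, 96-hour against weekly dressing changes and the lack of a common culture rule make this plausible. The documents do not tie cultures to dressing changes, however, and do not show that it happened.

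**Working it through.** The plan states no sample size, power, expected rate per 100 patient-months or culture frequency, so there is no figure to reproduce. What follows from the definition is exact. The sizes rest on assumed inputs.

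**Exact relations.** Let m be the mean number of positive cultures per infection.
- Reported rate = infection rate × m.
- Apparent rate ratio = true rate ratio × (m in silver ÷ m in control).

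The culture rate equals the culture-confirmed infection rate only when m = 1.

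**Control rates.** The Objective cites DLI in 10% to 50% of patients, with no time base. Assuming 24 months and a constant hazard, the rate per 100 patient-months is −100 × ln(1 − p)/24:
- p = 10%: 0.44
- p = 30%: 1.49 (about 1.5)
- p = 50%: 2.89 (about 2.9)

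**Reported rate at m = 3** (range for m = 1 to 4):
- 0.44 × 3 = 1.3 (0.44–1.8)
- 1.5 × 3 = 4.5 (1.5–6.0)
- 2.9 × 3 = 8.7 (2.9–11.6)

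**Simulation.** Assumed: 100 patients per arm, 18 months each, Poisson infections, and a geometric number (at least one) of positive cultures per infection. Per-patient counts were compared at two-sided 5% by t-test, tie-corrected Mann-Whitney, and linear regression on arm plus three covariates unrelated to outcome. There were 10,000 trials per main cell (Monte Carlo standard error at most 0.5 points).

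| Scenario | Test | 0.44 | 1.5 | 2.9 |
|---|---|---|---|---|
| Power at true ratio 0.5, m = 3 in both arms: infections counted → cultures counted | t-test | 20% → 14% | 57% → 39% | 85% → 64% |
| | Regression | 20% → 14% | 56% → 39% | 84% → 64% |
| | Mann-Whitney | 20% → 20% | 55% → 54% | 82% → 79% |
| False positives, no true effect, m = 3 control, 2 silver (apparent ratio 1 × 2/3 = 0.67) | t-test, regression | 6% | 18% | 33% |
| | Mann-Whitney | 5% | 6% | 8% |
| Power at true ratio 0.5, m = 2 control, 3 silver (apparent ratio 0.5 × 3/2 = 0.75): infections → cultures | t-test | 19% → 9% | 57% → 14% | 85% → 19% |
| | Mann-Whitney | 19% → 18% | 54% → 48% | 81% → 67% |

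With m = 3 in both arms and no true effect, all three tests reject in 4.2%–5.1% of trials, so equal culturing does not inflate type I error.

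**Smaller trials.** In the 3-against-2 scenario, t-test false positives are 4%, 10% and 18% at 50 per arm, and 1%, 6% and 9% at 25 per arm. Mann-Whitney stays at 4%–7%.

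**Which test applies.** The share of control patients with no infection at 18 months is exp(−18 × rate/100): 92%, 76% and 59%. Mann-Whitney is therefore the likely unadjusted test. That does not settle the matter, because the SAP's Conclusion says "The univariate analysis will provide preliminary insights into dressing effect" and treats the multivariate models as the more rigorous step. The only adjusted model named is linear regression, with no alternative if its residual checks fail.

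**A 60-day episode rule in the same model.** With positive cultures of one infection 7–21 days apart on average (assumed), the rule counts 0.94–1.08 episodes per infection, against 2.8–2.9 cultures. In the 3-against-2 scenario the apparent ratio becomes 0.95–1.01 and t-test rejection 4.6%–5.6%. In the equal-culturing scenario t-test power returns to 18%–20%, 52%–56% and 80%–82%.

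**The case against.** The best counter-reading is that the SAP is giving a case definition: a DLI is a culture-positive event, and one count per infection was meant. The label, Section D and the secondary outcome, which treats the first positive culture as the first infection, all fit that reading. It may well be the intention. It is not written, and the literal rule gives a different number, so this stands as a reason to state the rule and not as a reason to leave it.

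The sizes can also be challenged, largely with justice:
- A mean of 3 cultures per infection has no basis in the documents, and at 1 the problem vanishes.
- 100 per arm is at the high end for a single-centre trial. At 25 per arm, or at the lowest infection rate, the false-positive risk is near nil.
- Mann-Whitney largely protects the p-value, except when silver infections are cultured more often at a high infection rate. It does not protect the reported rate or rate ratio.
- Using linear regression for such counts is a separate issue, and part of the regression loss belongs to it.
- The simulation gives everyone equal follow-up, whereas the enrolment and closing dates imply roughly 12 to 36 months.

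The 60-day window is imperfect too. If cultures are 30–60 days apart on average, it counts 1.1–1.4 episodes per infection, and the 3-against-2 scenario gives an apparent ratio of about 0.86–0.94. That is still much closer to 1 than the 0.67 from raw counts. The rule also merges a new organism into an open episode, and it leaves DLI defined by culture alone, so colonisation would count and culture-negative infection would not.

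**Conclusion.** The concern holds and should be fixed. The written primary rule does not measure the objective's DLI rate unless every infection yields exactly one counted positive culture. That conclusion rests on the text and needs no assumed input.

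The practical size is conditional. Under equal culturing the effects are an inflated headline rate (threefold at m = 3) and, at 100 per arm, a loss of about 6 to 21 points of t-test or regression power, with the rate ratio unbiased and type I error unaffected. Under unequal culturing the ratio itself is biased. Over 25–100 per arm and 12–24 months, t-test false positives in the 3-against-2 scenario run 0.5%–8%, 4%–24% and 7%–44% at the three control rates; Mann-Whitney runs 2%–5%, 5%–6% and 6%–12%. Unequal culturing is a plausible risk, not a demonstrated fact.

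**What to change.** Replace the primary-outcome definition with wording such as:

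> Number of distinct culture-confirmed DLI episodes per 100 patient-months on support. A positive culture opens a new episode only if more than 60 days have passed since that patient's last positive culture; any other positive culture belongs to the open episode.

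The 60 days is an assumed counting window, not a treatment rule. The sponsor may choose another; 30 and 90 days serve as sensitivity analyses. In addition:
- Sign and date the rule before any comparison by arm.
- Have someone who does not know the arm code the episodes, from patient code, culture date and result only.
- Keep the positive-culture count as a supportive outcome, and report positive cultures per episode by arm.
- If repeat culture dates were not kept, count the first DLI per patient, with time at risk ending at that event.
- Disclose that the definition was clarified after follow-up closed. The document is dated 24 March 2025 and follow-up ended on 31 December 2024.

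The cost is one definition and a re-coding of culture records; the documents do not confirm that all repeat dates exist. There will be fewer nominal events and a lower headline rate. The window is a judgement: with cultures 7–21 days apart, 30 days splits some infections (0.99–1.39 episodes per infection) and 90 days merges some (0.91–1.00). The first-DLI fallback changes the estimand, overlaps the secondary outcome and lowers Mann-Whitney power slightly (20%, 53%, 77% instead of 20%, 55%, 82%). Neither version corrects differences between arms in whether an infection is cultured at all.

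### Both outcomes count a driveline infection only if a culture is positive, while only one arm wears an antimicrobial patch; a lower culture yield could pass for fewer infections

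*Combined protocol and SAP*

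**What the plan says.** In section F (SAP), the primary outcome is a DLI rate, "defined as number of driveline cultures positive for bacterial infection per 100 months of patients on support". The secondary outcome is "Mean time to first driveline infection, defined as a number of days to first positive culture". Neither has a clinical criterion.

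Section C (Interventions) describes the kits. The standard silver kit has "a silverlon antimicrobial patch, CHG swabs for cleaning, an occlusive dressing with window, and driveline anchors"; the standard control kit has "No antimicrobial barrier, CHG swabs for cleaning, an occlusive dressing with window, and driveline anchors". The sensitive-skin kits differ between arms in the same way on this point: a silver patch in one, no antimicrobial barrier in the other. The cleaning swab is the same in matching kits. For the silver arm, "The driveline dressing change frequency will be weekly"; the control interval is 96 hours.

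Section A (Inclusion Criteria) takes a broader view of DLI at entry for patients with an existing device: "Implanted prior to January 1st 2022 with no history or signs and symptoms of DLI as of January 1st 2022".

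The opening paragraph of Methods says that adverse events, culture results, a patient survey and driveline photos are collected. The SAP's Sensitivity Analyses paragraph covers only missing data and outliers. Nowhere does the document say what prompts a culture, how or where the swab is taken, or whether the procedure is the same in both arms.

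**The concern.** The stated objective is to reduce DLI, but what is counted is bacterial growth. The component under test acts against the organisms whose growth is the endpoint. The intervention could therefore change whether an infection is detected as well as whether it occurs, and the two would look the same in the primary rate and in the time to first positive culture. A patient with clear signs of DLI and a negative culture would be counted as uninfected.

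Nothing in the planned analysis would show this. Randomisation, a larger sample and adjustment for BMI, gender and INTERMACS level do not correct an outcome whose measurement depends on the arm. The Objective section hopes that the trial will help to standardise dressing practice, so readers will need to know whether a difference reflects prevention or detection.

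**Working it through.** **The plan's own figure.** There is none to reproduce: the document gives no sample size, event count, target effect, power or culture yield.

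**Inputs from the document.** Culture-only outcomes (section F); patch in the silver arm only, and dressing changes every 7 days against every 4 days (section C); significance level 0.05 (section F; two-sided is assumed, since this is not stated).

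**Assumed inputs.** Equal true DLI rates in the two arms; 30 expected culture-positive events in the control arm; a relative yield k, the chance that a silver-arm DLI is sampled and grows divided by the same chance in the control arm. The document gives no value of k, and k = 1 means no bias.

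**Step 1: effect on the rate ratio.** Let the true rate be λ in both arms and the control detection probability s. The observed rates are λs in control and λsk in silver, so the observed ratio is λsk / λs = k. Values of 0.9, 0.8 and 0.7 give apparent reductions of 10%, 20% and 30% with no true effect.

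**Step 2: chance of a significant result favouring silver.** With E control events, z = ln(k) / √(1/E + 1/(kE)), and the probability is Φ(−1.96 − z). For E = 30:

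| k | ln(k) | standard error | z | probability |
|---|---|---|---|---|
| 1.0 | 0 | √(1/30 + 1/30) = 0.258 | 0 | 2.5% |
| 0.9 | −0.105 | √(1/30 + 1/27) = 0.265 | −0.397 | 5.9% |
| 0.8 | −0.223 | √(1/30 + 1/24) = 0.274 | −0.815 | 12.6% |
| 0.7 | −0.357 | √(1/30 + 1/21) = 0.285 | −1.254 | 24.0% |

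**Step 3: dependence on the assumed event count.** The same formula gives:

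| Control events | k = 0.9 | k = 0.75 |
|---|---|---|
| 10 | 4.2% | 8.6% |
| 20 | 5.1% | 13.2% |
| 40 | 6.7% | 22.1% |

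The apparent reduction is the same at every event count. The chance that it reaches significance grows with the number of events.

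**Step 4: the dressing-change route.** Weekly changes are 365.25/7 = 52.2 a year and four-day changes 365.25/4 = 91.3, a ratio of 0.57. If detection depended on changes alone, the mean wait to the next change would be 7/2 = 3.5 days against 4/2 = 2 days. That is a delay of 1.5 days, not a lost event, unless the infection resolves in between.

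**The case against.** The strongest reply is that the mechanism is not documented. A reader might infer that silver-arm swabs are taken from under the patch, and that the primary result is therefore biased towards silver. The document supports neither step. It does not say where swabs are taken or whether the site is cleaned first, and it gives no evidence that silver lowers the yield from an established infection. Controls are also cleaned more often, which could lower their yield too. This stands: the bias is possible and its size could be nil. It does not remove the point, because the plan has neither a common sampling procedure nor an analysis that would show the problem.

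A reader might also treat the 52 against 91 changes a year as a large loss of detection in the silver arm. That is not supported. Dressings in both arms have a window, photos and adverse events are collected without distinction by arm, and no text links swabs to changes. This is at most a minor secondary route.

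The probabilities come from a log-rate-ratio test with an assumed event count. The SAP names t or Mann-Whitney tests, chi-square or Fisher's exact tests, and linear regression. The probabilities therefore show direction and order of size, and are not an error rate for this trial.

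Finally, a reader might conclude that a clinical definition should replace the primary outcome. The document does not support that either. The entry criterion mentions signs and symptoms without defining them, and no blinding is described. The document is dated 03/24/2025, after planned follow-up closed on December 31st 2024. A switch now would be post hoc and would exchange a possible laboratory bias for a possible observer bias.

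**Conclusion.** The point holds as a conditional limitation. Both outcomes depend wholly on a positive culture, only one arm has an antimicrobial at the site, and the plan neither standardises culturing nor tests the result against a DLI definition that does not depend on culture. If relative yield is k, the observed rate ratio under no true effect is k. With 30 assumed control events, the chance of a significant result favouring silver goes from 2.5% at k = 1 to about 24% at k = 0.7. The document does not give k, so neither the presence nor the size of a bias is established; if there is one, it most plausibly favours silver. What the document does establish is that a culture-only difference would be reported as a reduction in DLI, which is a wider claim than the measurement supports.

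**What to change.** Keep the culture-positive rate as the primary outcome, and make three additions.

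1. Add to the SAP's Sensitivity Analyses a named analysis that counts every DLI recorded in the adverse event collection, whether or not the culture grew. Assess events from adverse event records and driveline photos without knowledge of arm where feasible. State when the analysis was added relative to data review.
2. Report by arm the number of cultures taken per 100 patient-months and the percentage positive. This requires that negative cultures were retained. Present it as description only: silver could have fewer cultures and a lower percentage positive either because it prevents infection or because it suppresses growth or sampling.
3. State the conclusion as an effect on culture-positive DLI unless the clinical-definition analysis agrees.

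The cost is SAP wording, one analysis, one table and the time to review records and photos that Methods says are already collected. It should be checked that the adverse event records do capture culture-negative DLI; the document does not say so. The downside is that clinical signs are more subjective in a trial with no described blinding, and that the analysis comes after planned follow-up ended. It is therefore supportive and does not replace the primary.
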